10.5. Reconciliation of consent forms and research samples

These processes will be the same as those described in **9.1.5**. However the communication code **CP2** (rather than CP1) will be added to the donor record, together with the study outcome. Update PULSE donor records with 'outcome of donation' and add the communication code (**CP1**) on the donor record. Furthermore it will not be necessary to write a note on the DHC to prompt the Donor Records Team to add a temporary message to the donor record indicating that a research sample must be taken at the next visit.

10.6. Transport of Samples

The process for the transport of samples will be the same as that described in **Section 9.1.6**.

10.7 Post-donation questionnaire

Within two weeks of enrolling on the study donors will receive an email from the UoC Study Data Manager (see **Annex 2.5** COMPARE Email welcome and questionnaire (Stage 1, Visit 1 and Stage 2) V2 26.10.2015) with an online (URL) link to a study questionnaire. The URL-link will contain a unique custom tag which will be used to anonymously track questionnaire completion and to verify that it has been completed by the intended recipient. The participant

will also receive a separate email with the questionnaire password (see **Annex 2.6** COMPARE Email_questionnaire key_V1 13.08.2015). If the participant does not provide their responses to the questionnaire they will be sent an email reminder after 7 days (see **Annex 2.7** COMPARE Email_questionnaire reminder 1 (Stage 1, visit 1 and Stage 2) V2 26.10.2015). A second email reminder will be sent after a further 14 days (see **Annex 2.8** COMPARE Email_questionnaire reminder 2 (Stage 1, visit 1 and Stage 2) V2 26.10.2015). If the questionnaire has not been completed 7 days after reminder 2, then a text reminder will be sent (see **Annex 2.9** COMPARE questionnaire text reminder (Stage 1 and Stage 2) V1 17.12.2015)

The questionnaire will include:

Section 1

Questions about the general demographic characteristics of the participant

Section 2

The validated Fitzpatrick questionnaire for skin type assessment

Section 3

Questions about participants' experiences and preference of current and alternative methods for pre-donation haemoglobin measurements

Section 4

Questions regarding the symptoms of iron deficiency

Section 5

The validated Medical Outcomes Survey SF-36 version 2 for general health and wellbeing

Section 6

Questions regarding general adverse blood donation outcomes, e.g. breathlessness and fainting, including the validated short-form Blood Donors Reaction Inventory (BDRI)

Section 7

Questions regarding the lifestyle habits of donors, e.g. smoking, alcohol intake, dietary intake in general and of iron-containing foods in particular, and physical activity

Completion of the study questionnaire is not essential to remain part of the study, however a maximum of two reminder emails will be sent to participants who do not complete it (see above).

On completion of the questionnaire the participant will be taken to a 'thank you' web page.

11. Data management

11.1 Data management processes at mobile sessions

11.1.1 Donor record management

Mobile session staff will place a communication code (**CP1** or **CP2**) on the records of donors who enrol on Stage 1 or Stage 2 of the study respectively. This communication code will flag a donor's participation in the study and result in daily business objects (BoBs) reports being generated by NHSBT from their national database, PULSE. These BoBs reports (described in more detail in **Section 11.3.1**) will include data on enrolled donors and will be sent to the UoC COMPARE Data Manager for the purposes of managing the study protocols, tracking study participation and populating the research database in an efficient and secure way.

Mobile session staff will also write a note on Stage 1 participants' DHCs to prompt the Donor Records Team to add a temporary message to the donor record. The temporary message will appear on the donor's DHC, which they take with their 2nd study blood donation visit, and will indicate to the mobile team staff that a research sample must be taken.

11.1.2 Electronic transfer of data from non-invasive measurements

At the end of the day, members of the mobile team will upload any data collected from the non-invasive devices to a secure NHSBT server site that can be viewed by study staff with NHSBT honorary contracts. The data will consist of the haemoglobin measurement(s), a time and date stamp and the Donor Number. The data will, therefore, consist of minimal personal identifiable detail. Once the data have been uploaded, the mobile team will send an email of notification to the UoC Helpdesk and Data Manager.

11.1.3 Transfer of consent forms

At the end of the day, members of the mobile team will post consent forms and reconciliation checklists to the NHSBT administration team. NB: If no donors have been recruited, the donor carer will send an email to UK BioCentre, cc'd to the admin team and UoC.

11.2 Data management process at NHSBT Administration Team

On receipt of consent forms and reconciliation checklists from NHSBT mobile teams, the administration team will cross-check the number of consent forms with the information on the study-specific reconciliation checklist. Consent forms and checklists will then be scanned and placed onto a server drive that can be viewed by study staff with NHSBT honorary contracts. Consent forms and checklists will be organised on the server drive both by mobile team and by date. Paper copies will be kept in a secure place until the end of the study when they will be sent to UoC Study Team for long-term storage.

Every day, the UoC Data Manager will receive a BoBs report (see above) generated from PULSE which will include the number of donors who have consented to the study. Once donor numbers have been reconciled between the BoBs report and consent forms, the Data Manager will generate a unique study ID for each donor and email the online study questionnaire. If donor numbers cannot be reconciled, the Data Manager will investigate the audit trail for a possible explanation and solution. The actions to be taken in the event of non-reconciliation are documented in **Annex 1: Flowchart 4**.

11.3 Data management processes at University of Cambridge

11.3.1. Population and management of research database

The UoC Data Manager will receive a set of PULSE Business Objects reports (**BoBs#1 - #6**) from NHSBT containing data for the purposes of managing the study protocols, tracking

study participation and population of the research database in an efficient and secure way. The data to be exchanged are fully described in **Annex 2.21** (URS COMPARE Business Objects Reports V1 13.08.2015). The reports will be in .csv format, to be saved as a zipped file with encryption known only by certain members of the UoC Research Study Team, and emailed to a nominated email address at UoC.

11.3.2. Reconciliation of research samples

The UoC Data Manager will receive a daily list from UK BioCentre containing the donation identification numbers (DINs)² retrieved from research sample tubes and the date of samples received. This report will be created in .csv format, saved as a zipped file with encryption known only by certain members of the UoC Research Study Team, and emailed to a nominated email address at UoC. The Data Manager will reconcile the number of DINs from the UK BioCentre report with the number of DINs from the PULSE reports (**BoBs#1 and #2** see **Annex 3**). The actions to be taken in the event of non-reconciliation are documented in **Annex 1: Flowchart 4**.

11.3.3 Transferring non-invasive measurement data to research database

Once the helpdesk receives notification from the mobile teams of non-invasive and HemoCue® data on the NHSBT server site, they will securely transfer it to the UoC Study Data Manager for secure storage on the COMPARE study research database.

11.4 Privacy and confidentiality of participant data Steps taken to protect participants' privacy and confidentiality include:

1. Personal information (including name and address) will be directly provided by study participants through the study online questionnaire. This information will be used to communicate with participants and will be held in a secure location, separately from the study data.
2. At the blood donation session, consent to take part in the study will be recorded on a form that will include identifiers including participant name. Scanned copies of consent forms, collected at the donation visit, will be transferred to the study coordinating centre at the University of Cambridge. This transfer will involve the use of NHSBT secure systems. The forms will be stored in a secure location, separately from the study data; in the long-term these data will be stored using an off-site storage facility (eg, Iron Mountain).
3. Limited personal information will be accessed and retrieved from the national NHSBT database (PULSE). This will include email address and telephone number for the purposes of study communication only. In addition we will retrieve participants' Donor Number and NHS number. These personal data will be stored in a secure location, separately to the study database. Access to this information will be password-protected and restricted to designated members of staff working under the direct supervision of the senior investigators.
4. Samples and data collected during the study will be stored using a unique, anonymous study identification number.

² The Donation Identification Number is unique to each donation and donor.

5. A table linking participants' anonymous study identification number to their Donor Number and NHS number will be stored on a separate password protected location which may be accessed by the Study Data Manager only. This link table, which may be accessed with the explicit approval of senior investigators, will be used to retrieve relevant health information from participants medical and other health-related records. The retrieved information will be pseudo-anonymised as any personal identifying details will have been removed and replaced by the unique anonymous study identification number. The applicants received ethical approval to retrieve electronic health records data, in the same way, in previous studies of blood donors, eg, the INTERVAL study [REC 11/EE/0538], Cambridge CardioResource (REC 09/H0304/42), and the donor-EHR study (REC 14/EE/0182).

6. All study data will be stored in restricted-access, study databases. This 'study database' will not be connected to the NHSBT database containing participants' personal details. The study data will be linked to the study identification number. Access to the study database will be password-protected and will be used only by named researchers working on this study under the direct supervision of the senior scientific investigators.

12. Future data collection

Participant data will be linked to various existing health records using the NHS number which will be included in the Business Object report (**BoBs#1**) received by UoC Data Manager from NHSBT. This will allow tracking of participants' health in the future and will provide relevant information to NHSBT on the long-term health consequences of blood donation. It will also offer wider scope to look at determinants of future health outcomes in the general population e.g. genetic variants and lifestyle factors.

13. Blood sample processing and analysis

Research blood samples collected at blood donation sessions will be transported to a purpose-built bio-repository, UK BioCentre (Milton Keynes and Stockport). This facility provides a proven service to academic and industrial partners conducting biomedical studies (most notably UK Biobank -a study in 500,000 people to study the causes of common diseases <http://www.ukbiobank.ac.uk/> and the INTERVAL study - a study in 50,000 blood donors to determine whether the interval between blood donations in England can be safely and acceptably decreased <http://www.interval.org.uk/>).

UK BioCentre holds a Human Tissue Authority License and complies with ISO 9001:2008 (Quality Management accreditation of services provision) and ISO 27001:2005 (Information Security Management accreditation of service provision – accreditation held at Stockport and pending at Milton Keynes).

UK BioCentre will support the study's processing and assay requirements. Blood samples will be collected at the registration visit and at the second visit for Stage 1 participants only. At each of these time-points UK BioCentre will:

1. Generate lists of samples received by scanning the DIN on sample labels and email these sample lists to the study centre in Cambridge. This will enable consolidation of the number of samples and number of consent forms retrieved (see **Section 11.3.2** above).
2. Use whole blood from the 4ml EDTA sample to generate an extended haematological profile of blood cell indices using a Sysmex Full Blood Count analyser. Aliquots of whole blood will be stored at -80°C for future use.
3. Sub-aliquot the 6ml serum sample into 2 x 0.8ml serum aliquots. These will be labelled with a unique study identifier linked to the DIN and stored at - 80°C for future research, including measurement of soluble biomarkers (e.g. ferritin, hepcidin) known to be related to iron or red cell metabolism
4. Sub-aliquot the 6ml EDTA sample into 2 x 0.8 ml plasma aliquots and buffy coat. The plasma will be stored at -80°C for future use. DNA will be extracted from the buffy coat. Extensive genotyping and/or sequencing will be done, including for genetic variants relevant to iron homeostasis and blood cell indices (e.g. variants in *HFE*, *TMPRSS6*, *TFR2*). DNA will be stored. These will be labelled with a unique study identifier linked to the DIN.
5. Storage of TEMPUS tubes at -80°C for future research
6. Store samples in an anonymised form. Access to the tables linking study identification numbers to a participant's identity will be stored on a separate password-protected system which may be accessed only with the explicit approval of senior investigators. A Data Access Committee will review written proposals for the use of samples and assess their scientific excellence. Stored samples will be labelled with the study identification number only therefore researchers using the samples will never know the identity of the person who donated the sample. The release of samples to other organisations and researchers will be regulated by a material transfer agreement.

13.1 Future use of stored samples

As stated above, we plan to collect 19ml of whole blood for research in four sample tubes i.e. 4ml EDTA, 6ml EDTA and 6ml serum sample and TEMPUS tubes. These will be collected at baseline study visits. Participants enrolled in the first stage of recruitment will also be asked to give research sample (4 ml) with their second routine donations.

The stored samples will provide an epidemiological bioresource that will, enable detailed study of the health of blood donors. More generally, this resource will encourage future

studies in NHSBT that address other relevant service needs. These subsidiary studies could help advance scientific understanding and public health, addressing existing and unanticipated hypotheses which the current applicants may carry out with other academic and/or industrial collaborators.

Future use of samples will include carrying out biomarker measurements in the stored plasma/serum samples and using current and/or future genotyping or sequencing technologies that assay stored DNA samples. Specifically, samples will be used for:

1. Analysis, amplification and storage of DNA extracted from blood: including tests that will look at DNA sequence variation e.g. genotyping tests, genomic hybridization arrays and sequencing of a part or the whole genome, and the analysis of RNA by sequencing or expression arrays.
2. Analysis and storage (indefinitely) of blood cells, blood components or derivatives for future use in research: including the isolation and storage of any type of cell (e.g. red blood cells) and other components found in plasma and serum such as proteins, carbohydrates and lipids and performing biochemical and chemical tests on these.

Biological materials and derivatives will be exchanged with collaborating research and NHS/private sector laboratories in the UK and abroad. In the case of exchange of materials with non-named study collaborators, a material transfer agreement will be used to regulate the transfer of materials and to regulate adherence to the principles of good guardianship. Collaborating partners will also have a range of laboratory tests that include, but are not restricted to studying cellular and biochemical parameters and analysis of DNA and RNA as stated above. This may include genome wide analysis of SNPs and/or re-sequencing of genes and testing serum/plasma factors.

Samples and data which will include a participant's full DNA (genetic) code may be used in a number of approved research projects. The results of these projects may not be known for several years. As sample measurements are not performed in the same way or to the same laboratory standards as clinical tests, participants will not be informed of any incidental findings. Researchers using these samples will only be provided with anonymised data which ensures they cannot link the sample or data to a participant by name.

14 Safety reporting

14.1 Donation deferrals

NHSBT will run a daily automated PULSE query to provide the UoC Data Manager with a report detailing deferrals in study participants (see **Annex 2.21: BoBs#3**). This report will include Donor ID (Donor Number), deferral date and deferral code. These data will be emailed as an encrypted csv file to a study-specific UoC email address. These data will be reported to the Study Steering Committee at intervals to be specified by this committee.

14.2 Adverse events of donation (AEDs)

AEDs during the donation visit (e.g. faints) will be dealt with using NHSBT systems which are currently in operation i.e. the event will initially be recorded on the DHC and later uploaded to the PULSE database.

AEDs occurring after the donation visit and reported to NHSBT will be referred to the Clinical Support Team. Events will be recorded on the PULSE database.

NHSBT will run an automated PULSE query to provide UoC Data Manager with a report detailing adverse events AEDs (see **Annex 2.21: BoBs#4**). This report will include AEs occurring during or after the donation visit (e.g. faints) and recorded by NHSBT on PULSE. This report will include Donor ID (donor number), AE date and AE code.

These data will be reported to the Study Steering Committee at intervals to be specified by this committee.

14.3 Serious adverse events

14.3.1 Definition of a serious adverse event (SAE)

An adverse even on any treatment that:

1. Results in death
2. Is life threatening (the term “life-threatening” refers to an event in which the participant was at risk of death at the time of the event. It does not refer to an event that hypothetically might have caused death if it was more severe)
3. Requires patient hospitalisation
4. Results in persistent or significant disability/incapacity

14.3.2 Death

NHSBT will provide the UoC Data Manager with a report (see **Annex 2.21: BoBs#5**) which will include the donor numbers of any participants who die during the study and details on cause of death (if available). Deaths will be reported to the Study Steering Group who will monitor the rate and causes (if available) of death.

14.3.3 Serious adverse events of donation (SAEDs)

Any SAEDs are recorded by NHSBT and will be reported to UoC, on a case-by-case basis, by the NHSBT Operational Change Manager. These incidents will be reported to the Study Steering Committee.

For further details of reporting procedures for serious adverse events, see **Annex 1: Flowcharts 8b – 8d**.

15. Withdrawals

15.1 Identifying level of withdrawal

All requests from donors to withdraw from the study will be directed to the research study team

A participant is free to withdraw their consent from the study, at any time, without giving a reason. Participants will be able to choose their desired level of withdrawal after discussion with the study team; there are two options:

15.2 No further contact

This will mean that the participant will no longer be contacted by the study team but will continue to give their permission to retain and use information and samples provided previously and to obtain and use further information from health records. Participants will be required to complete a form indicating these wishes (see **Annex 2.22** COMPARE withdrawal (no further contact) V1 13.08.15)

15.3 No further use

This will mean that the participant withdraws their permission:

1. to be contacted by the study team
2. for further information about them to be collected
3. for previously collected information and samples to be made available to researchers

If a participant requests no further use it will not be possible to remove results of any tests already obtained from samples from the study database, but we will prevent records from being used in any future research. Blood samples will be removed from the central study repository after receiving written notification of withdrawal. However it will not be possible to remove small volumes of samples which already have been distributed to research laboratories but results which are generated after withdrawal will not be uploaded to the study database. Participants will be required to complete a form indicating these wishes (see **Annex 2.23** COMPARE withdrawal (no further use) V1 13.08.15).

15.4 Positive microbiology

The University of Cambridge will be notified by NHSBT of any donors who test positive for routine microbiology tests conducted by the blood service. These donors will no longer be eligible to donate blood and therefore will be withdrawn from the project.

15.5 Recording withdrawals

The UoC Study Data Manager will place a flag on the research database to ensure appropriate use of data and will notify the helpdesk of withdrawal. The helpdesk will add a communications code (**CP3**) to the PULSE database to indicate the donor is no longer taking part in the study, and change the donor procedure code back to WHB (whole blood) and move the donor to an appropriate subpanel to ensure their next appointment at the standard donation interval.

University of Cambridge research staff will instruct UK BioCentre to remove all archive samples from the bio-repository for donors who have requested no further use and for participants who have been withdrawn from the study due a positive microbiology result.

Signed withdrawal forms will be kept as a record of the participant's wishes.

[figure not shown]
16. Sample size and statistical analysis plan

16.1 Sample size

The overall study sample size has been determined on the basis of the following (partially overlapping) considerations: (i) the need to generate evidence sufficiently compelling to influence regulators and policy-makers; (ii) NHSBT's duty of care to 1.3 million blood donors per year, making it vital for the service to evaluate even subtle changes in the proportion of donors that are bleed with an haemoglobin levels below the recommended threshold; (iii) NHSBT's objective to move toward a more donor-friendly way of haemoglobin testing, that can improve donor's experience and optimise donor session flow.

Our power calculation is based on having 80% power to detect a 10% relative difference in false pass rate between the current NHSBT screening method and either: (i) Hemocue® on capillary blood; (ii) a "post-donation" screening strategy, or (iii) a non-invasive strategy to measure pre-donation haemoglobin concentration. The sample size calculations are based on a direct (ie, within person) comparison using a McNemar's paired test. Using information on a previous study and on INTERVAL data, we assumed a prevalence of "true" low haemoglobin of 10%, a sensitivity of the current NHSBT screening method of 55%, and a correlation coefficient between current method and any alternative novel strategies of 0.70 (**Figure 3**). Similar sample size will be required for the indirect (ie, between person) comparison of non-invasive devices (MBR Haemospect® vs Orsense NBM 200®), assuming that the sensitivity of non-invasive devices is about 20% (as reported by previous publications).

Figure 3. Sample size required for a within-person pairwise comparison to detect relative differences in false pass rate for low haemoglobin between screening strategies with 80% power

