Stage 2: One of the new methods to be evaluated (ie, non-invasive spectrometry) involves a choice between two commercially-available devices. It would be ideal to conduct a head-to-head comparison of these two devices in the same set of participants as the other methods are to be compared in. Unfortunately such an approach would likely be too time-consuming and disruptive to NHSBT’s high-throughput service. Hence, we plan a second stage of recruitment that will involve enrolment of a further approximately 13,000 participants, focusing on the comparison of two different non-invasive spectrometry devices. During the second stage of recruitment, selection of mobile donation centres will be done in a way to over-sample donors of non-European ancestry (eg, those of African, Middle Eastern, and South Asian ancestry). The rationale is that the performance of non-invasive spectrometry devices is known to differ in people with different skin colour and tone.

Figure 1: Study design

^a assuming ~30% drop-out rate 18,000 donors need to be recruited at the previous donation visit.

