4.3.2 Secondary endpoint

We will study the following important and pre-specified secondary endpoints:

- 1) differences in the proportion of donors who would have been inappropriately bled when comparing the various newer methods to be studied with one another
- 2) differences in the proportion of donors who would have been inappropriately bled when comparing the two non-invasive devices to be studied with each other
- 3) feasibility and acceptability of different methods, according to the views of blood donors and blood services staff
- 4) cost-effectiveness of different methods
- 5) variability of the performance of different methods by donors' personal characteristics. Examples of key characteristics include: donor status (repeat versus first-time blood donor), sex, menopausal status (for women), skin colour tone, biological profile (such as measurement of genetic variants [eg, HFE, TMPRSS6, TFR2], soluble biomarkers [eg, ferritin, hepcidin] known to be related to iron or red blood cell metabolism and other DNA and blood-based biomarkers that could define relevant subpopulations)
- 6) medium and long-term health consequences of inappropriately bleeding at donation via, for example, linking participants' study information with a variety of electronic health records (such as those available through the Health and Social Care Information Centre)

Participants who enrol in COMPARE will also be part of a bioresource of healthy volunteers, and samples and data will be used in future approved research projects looking at donor and public health.

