16.2 Statistical analysis plan

For comparison of alternative novel strategies versus the current NHSBT screening strategy, analyses will involve only within-person comparisons. Differences in sensitivity (Se) and specificity (Spe) (measured against the gold standard) of the novel screening methods versus the current methods will be calculated. In order to clarify the impact of a given difference in sensitivity and specificity between devices in terms of donor screening, difference in false pass rate (FPR) will also be calculated (**Box 1**). Further within-person (direct) comparisons will be conducted to assess differences in sensitivity and specificity in the novel screening methods amongst individuals that have both novel screening methods of

interest assessed. In comparison of non-invasive devices (MBR Haemospect® vs Orsense NBM 200®), analyses will involve between-person comparisons. To assess the performance of the Sysmex auto-analyser as a “gold standard” haemoglobin measurement, we will test 10% of samples in duplicates.

Box 1. Definitions of key statistical metrics used for analysis

Screening strategy	Sysmex auto-analyser (“gold standard”)	
	Positive (Low Hb)	Negative (Sufficient Hb)
Positive test result (Low Hb)	True Positive (TP)	False Positive (FP)
Negative test result (Sufficient Hb)	False Negative (FN)	True Negative (TN)

Hb, haemoglobin

Sensitivity = probability of detecting low Hb given the donor truly has low Hb
 = probability of testing positive given the donor is true positive (has low Hb)
 = $TP / (TP+FN)$

Specificity = probability of detecting sufficient Hb given the donor truly has sufficient Hb
 = probability of testing negative given the donor is true negative (Sufficient Hb)
 = $TN / (TN+FP)$

False Pass Rate = probability of inappropriately bleeding a donor
 = $FN / (TP+FP+TN+FN)$

17. Finance and insurance arrangements

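### On the endpoint the protocol lists, a sample size similar to the paired one gives the between-person device comparison about 41% to 67% power, not 80%

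*Protocol*

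**What the plan says.** Section 16.1 of the Protocol sets the target as "80% power to detect a 10% relative difference in false pass rate" between the current method and each alternative. It says the "sample size calculations are based on a direct (ie, within person) comparison" using McNemar's test, with 10% prevalence of true low haemoglobin, 55% sensitivity of the current method and a correlation of 0.70. For the two non-invasive devices it adds only "Similar sample size will be required for the indirect (ie, between person) comparison of non-invasive devices", with device sensitivity taken as about 20%.

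The device comparison is secondary endpoint 2 in Section 4.3.2: "differences in the proportion of donors who would have been inappropriately bled when comparing the two non-invasive devices to be studied with each other". Box 1 in Section 16.2 gives the matching metric, "False Pass Rate = probability of inappropriately bleeding a donor", as FN divided by the sum of all four cells, so over all donors. Section 16.2 also says the device comparison is between persons.

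Section 4.2 gives the numbers. About 12,500 donors attend Stage 1 visit 2 and each gets one of the two devices. Stage 2 adds "enrolment of a further approximately 13,000 participants" and focuses on the device comparison.

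**The concern.** Pairing reduces the sample size because each donor serves as his or her own control and the two results are correlated. Two separate groups of donors do not have that advantage. On a rate of about 8% over all donors, an unpaired comparison should need far more donors than a paired one, so the word similar calls for a check.

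Stage 2 recruits about 13,000 people mainly for this question. If the comparison falls well short of 80% power on its listed endpoint, a null result could be taken to show that the devices perform alike when the study could not have told them apart.

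**Working it through.** **Inputs from the protocol.** Prevalence of low haemoglobin 10%; sensitivity 55% (current method) and about 20% (devices); correlation 0.70; 80% power; 10% relative difference in false pass rate (all Section 16.1). Denominator: all donors (Box 1). Donors with a device reading: about 13,000 in Stage 2, and 12,500 + 13,000 = 25,500 with Stage 1 visit 2.

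**Assumptions, because the protocol gives no value.** Two-sided 5% test; 1:1 split between devices; independent donors. The 10% relative difference is stated for comparisons with the current method and is carried over, since no other effect is given for the devices.

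**1. Paired requirement.** False pass rate of the current method: 0.10 × 0.45 = 4.5%; a 10% relative reduction gives 4.05%.
- Both methods wrong: 0.045 × 0.0405 + 0.70 × √(0.045 × 0.955 × 0.0405 × 0.9595) = 0.0304.
- Discordant proportions 0.0146 and 0.0101; sum D = 0.02464; difference d = 0.0045.
- n = [1.960√D + 0.842√(D − d²)]² / d² ≈ 9,549. At alpha 0.05/3 (z = 2.394) it is 12,738.

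The planned 12,500 is therefore reasonable for the paired comparisons.

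**2. Unpaired requirement on the listed endpoint.** Device false pass rate: 0.10 × 0.80 = 8.0%; a 10% relative reduction gives 7.2%; mean 7.6%.
- n per device = [1.960√(2 × 0.076 × 0.924) + 0.842√(0.08 × 0.92 + 0.072 × 0.928)]² / 0.008² ≈ 17,223.
- Total about 34,400. That is 2.7 times 12,738 and 3.6 times 9,549, and more than the 31,000 donors to be enrolled.

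**3. Power with the planned numbers.** Power = Φ{[0.008√n − 1.960√(2 × 0.076 × 0.924)] / √(0.08 × 0.92 + 0.072 × 0.928)}.

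| Donors | n per device | Power, 8.0% v 7.2% | Power, 8.0% v 8.8% | Relative reduction detectable at 80% power |
|---|---|---|---|---|
| Stage 2 alone | 6,500 | 40.6% | 37.6% | about 16% |
| Both stages | 12,750 | 67.4% | 63.4% | about 11.6% |

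Simulation of 8.0% v 7.2% gave 40.6% and 67.7%.

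**4. Other assumptions (Stage 2 alone, then pooled).** One-sided 5%: 53.0% and 77.8%. Two-sided 0.05/3: 25.0% and 50.7%. Prevalence 5%: 22.1% and 38.6%. Prevalence 15%: 57.6% and 85.4%. Prevalence 20%: 71.9% and 94.5%.

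**5. The scale on which the sentence holds.** Among low-haemoglobin donors only, the miss rate is 80% v 72%.
- n = [1.960√(2 × 0.76 × 0.24) + 0.842√(0.80 × 0.20 + 0.72 × 0.28)]² / 0.08² ≈ 446 low-haemoglobin donors per device.
- At 10% prevalence that is about 4,460 donors per device, 8,920 in total.
- Stage 2 supplies 6,500 × 0.10 = 650 low-haemoglobin donors per device, with power of about 92%.

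**The case against.** The strongest reply is that the authors meant sensitivity. The only assumption Section 16.1 gives for the devices is a sensitivity. Section 16.2 puts sensitivity and specificity first, brings in the false pass rate to show their impact, and names no metric in its sentence on the devices. On the miss rate among low-haemoglobin donors the unpaired need is 8,924 donors in total (11,908 at alpha 0.05/3), within 7% of the paired 9,549 (12,738), so similar would be a fair word. That match does mix two denominators: if the 0.70 correlation applies among low-haemoglobin donors, the paired need is 5,736 or 7,655. More importantly, Section 16.1 and the caption of Figure 3 power on the false pass rate, Section 4.3.2 lists the proportion of donors inappropriately bled, and no section names sensitivity as the device test. The reply shows how cheaply the sentence can be put right, but it does not make it right for the listed endpoint.

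A second reply is that similar means about 12,500 per device. That is nearly the pooled case, and power is still about 67%.

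It also stands that alpha, allocation and the device effect are assumptions, that nothing confines the comparison to Stage 2, and that the pooled shortfall is modest (11.6% detectable against 10%).

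A reader might infer that the crude comparison will declare equally accurate devices different. Between persons, false pass rate = prevalence × miss rate, and in Stage 1 a donor gets whichever device the mobile team is using (Section 9.2.3). Prevalences of 10% and 11% with equal miss rates would give 8.0% v 8.8%. But that split is hypothetical: the protocol gives no prevalence by device group, and adjustment may well be set out in a separate analysis plan. The structure of the measure supports reporting a standardised rate; it does not support a claim that bias will occur.

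**Conclusion.** The sample-size sentence is wrong for the endpoint as listed. At the protocol's prevalence and sensitivity, with the assumptions above, the device comparison needs about 34,400 donors and has about 41% power in Stage 2 or about 67% pooled. At the stated 10% prevalence, none of the alpha and sidedness choices tried reaches 80%. The pooled comparison would exceed 80% at 15% prevalence, but the protocol assumes 10%. Any clustering of donors within teams would lower the figures further.

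Two stronger conclusions do not follow. The primary paired comparisons are not affected, since their requirement is consistent with 12,500. Nor is Stage 2 too small for every useful device comparison: on the miss rate among low-haemoglobin donors it has about 92% power. This concerns a secondary endpoint and should be fixed in the text; it gives no reason to change recruitment.

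**What to change.** In Section 16.1, replace the sentence on similar sample size with the alpha, effect size, denominator, contributing stages and resulting power for the device comparison. Then take one of two routes:

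- **Keep the false pass rate as the test.** State power of about 41% (Stage 2) or 67% (both stages) for a 10% relative difference, with about 16% or 11.6% detectable at 80% power.
- **Name sensitivity among donors with low Sysmex haemoglobin as the device test.** State about 446 such donors per device (about 4,460 donors per device, 8,920 in total) and about 92% power in Stage 2. Align secondary endpoint 2 in the Protocol Summary and Section 4.3.2, and Section 16.2, with it. Give the effect explicitly as a miss rate of 80% v 72% (sensitivity 20% v 28%), because a 10% relative difference in sensitivity itself (20% v 22%) would need about 130,200 donors.

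In either case, also report each device's false pass rate as (1 − sensitivity) × one prevalence pooled over both device groups, so that a difference in donor mix does not enter the comparison.

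The cost is a less favourable stated power on the first route, or a small change to the definition of a secondary endpoint on the second. Neither needs extra donors or measurements.
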